**A3a. Financial Conflict of Interest**

Does any member of study personnel (Investigator (including investigator's spouse and/or dependent children)) that are involved in the design, conduct, or reporting of the research have a Significant Financial Interest (SFI) that would reasonably appear to be affected by the research for which funding is sought and/or associated with an entity/business that would reasonably appear to be affected by the research?

No

**A5. Funding Source:**

Organization: VA CENTRAL OFFICE, RR&D

**A6a. Institution(s) where work will be performed:**

Michael E. DeBakey Veterans Affairs Medical Center

**A6b. Research conducted outside of the United States:**

Country:

Facility/Institution:

Contact/Investigator:

Phone Number:

If documentation of assurances has not been sent to the Office of Research, please explain:

**A7. Research Category:****A8. Therapeutic Intent**

Does this trial have therapeutic intent?

Yes

**Section B: Exempt Request****B. Exempt From IRB Review**

Not Applicable

**Section C: Background Information**

The process of recovery and community reintegration across the lifespan for Veterans with posttraumatic stress disorder (PTSD) and anxiety disorders (henceforth referred to as anxiety-based disorders) is a significant problem. Resuming and participating in major social life roles within the community is challenging due to the debilitating nature of anxiety, which often results in avoidance of everyday activities and social withdrawal. Consequences of untreated anxiety-based disorders range from substantial impairment in social, vocational, emotional and physical functioning to high rates of suicide.

Despite the effectiveness of evidence-based CBT for anxiety based disorders, a significant proportion of Veterans do not initiate treatment. Nationwide data indicate that less than 10% of recently deployed Veterans receive an adequate course of psychotherapy within the first year of being diagnosed with a mental health disorder. Avoidance associated with anxiety and fear-based disorders (e.g., PTSD) lead to low rates of treatment engagement and high rates of treatment dropout. For instance, attrition rates in PTSD treatment (20-40%) are similar to attrition rates (25%) for treatment of other disorders such as panic disorder and social anxiety disorder. Furthermore, length of time required to deliver evidence-based psychotherapies interferes with daily (family, work, school) activities and necessitate arranging time off work, scheduling around school schedules, and traveling to multiple appointments.

Novel and innovative approaches capable of improving community reintegration, quality of life, and clinical outcomes, while also keeping Veterans engaged in treatment are much needed. Given the impact PTSD and related anxiety disorders can have on family members, it is also important to learn about their perspectives regarding the advantages and disadvantages of new treatment approaches.

**Section D: Purpose and Objectives**

The overall objective of the proposed study is to improve reintegration across the lifespan and quality of life in Veterans with anxiety-based disorders including co-occurring depression. A randomized controlled trial will test the effectiveness of transdiagnostic group CBT delivered in an intensive weekend format. This transdiagnostic protocol addresses multiple anxiety-based disorders in a single protocol by incorporating general core components of CBT with additional skills-based modules that can be flexibly tailored to any anxiety disorder. Intensive CBT (iCBT) is an innovative and promising method of treatment delivery with the potential to produce rapid improvement in functional and clinical outcomes. The compressed format (e.g., weekend) of iCBT increases the likelihood that Veterans will engage in and complete treatment. During the course of the study, we will also gather qualitative data from Veterans who participated in the weekend treatment (and their family members) to obtain a deeper understanding of how iCBT and environmental barriers and facilitators have impacted their overall functioning and quality of life.

## **Section E: Protocol Risks/Subjects**

### **E1. Risk Category**

Category 1: Research not involving greater than minimum risk.

### **E2. Subjects**

Gender:

Both

Age:

Adult (18-64 yrs), Geriatric (65+ yrs)

Ethnicity:

All Ethnicities

Primary Language:

English

Groups to be recruited will include:

Patients

Which if any of the following vulnerable populations will be recruited as subjects?

Mentally ill

Vulnerable populations require special protections. How will you obtain informed consent, protect subject confidentiality, and prevent undue coercion?

Project staff will review the consent form with the patient, including the study procedure, patient's rights, risks and benefits of participation, and the methods that will be taken to protect the patient's confidentiality. The patient will have the opportunity to ask questions throughout the process. Each patient will be given his/her own copy of the informed consent form to follow along by during the consent process and to keep for future reference. Patients will be asked to reiterate their understanding of the important points of the consent form to ensure that full informed consent is obtained. Study staff will clarify any necessary points and answer questions. Participants will not require a Legally Authorized Representative for this study.

### **E3. Pregnant woman/fetus**

Will pregnant women and/or fetuses (as described in 45 CFR 46 Subpart B) be enrolled in the research?

No

### **E4. Neonates**

Will neonates of uncertain viability or nonviable neonates (as described in 45 CFR 46 Subpart B) be enrolled in the research?

No

### **E5. Children**

Will children be enrolled in the research?

No

## **Section F: Design/Procedure**

### **F1. Design**

Select one category that most adequately describes your research:

c) Pilot

Discuss the research design including but not limited to such issues as: probability of group assignment, potential for subject to be randomized to placebo group, use of control subjects, etc.

The clinical trial will compare the effectiveness of iCBT to standard CBT (sCBT) and treatment as usual (TAU). A total of 252 Veterans from all war eras will be recruited who have at least one of the following disorders: PTSD, panic disorder (PD), social anxiety disorder (SAD) and generalized anxiety disorder (GAD). Veterans with or without co-occurring depression will be included. Participants will be randomized to iCBT, sCBT, or TAU. The study design uses unequal randomization to the active intervention arms and to treatment as usual to reduce unnecessary recruitment. Thus, the percent chance that participants will be randomized to one of the three conditions are: 37% iCBT, 37% sCBT, and 24%TAU. Participants in iCBT will receive treatment over one weekend (16 total session hours); those in sCBT will receive the same treatment weekly, over 12 weeks (16 total session hours); and those assigned to TAU will receive routine clinical care. Assessments will be completed at four time points: baseline, 1-month, 3-months, and 6-months.

This protocol should be considered minimal risk because the likelihood and degree of discomfort anticipated in this intervention are lower than what people would encounter in daily life. This is a non-invasive behavioral intervention that is designed as a two-day workshop to teach participants about anxiety and provide them with opportunities to practice examining and adjusting their thoughts based on evidence. Participants have the benefit of having trained therapists available to guide and help them engage in these exercises. The workshop is similar to other classes and seminars people may attend in daily life. The room is set up as a classroom with individual desks and chairs for participants. Breaks are scheduled throughout the day, and participants are informed that they may take a break whenever they need.

It is important to note that the content of the treatment protocol is not new; cognitive behavioral therapy (CBT) is a well-established, empirically supported treatment for anxiety and mood disorders. In fact, it is the gold-standard treatment and recommended by NIMH as a first line intervention for anxiety and mood disorders. The PI of this study has been offering weekend CBT for anxiety disorders at the MEDVAMC for the past 10 years. The compressed weekend format for delivering this treatment has been established across several clinical trials to be a safe and feasible method of providing treatment. Veterans report high satisfaction with this treatment format and prefer it over standard weekly sessions ([name] et al, 2015, Journal of Anxiety Disorders, 33, 1-7). All of these factors support the rationale that the protocol should be considered minimal risk.

Inclusion Criteria:

(1) Veteran at least 18 years old; (2) current diagnosis of at least one anxiety-based disorder: PTSD, PD, SAD, or GAD (based on ADIS-5); (3) moderate-to-poor life enjoyment and satisfaction as indicated by a score of 42 or lower on the Q-LES-Q-SF (4) stable on psychotropic medication for 4 weeks before study participation; and (5) willing to be randomized to treatment condition. Inclusion criteria for family members of Veterans randomized to the weekend intervention who wish to participate in the qualitative interview: (1) at least 18 years old and (2) has regular contact with the Veteran (e.g., sees or talks with Veteran several days/week).

Exclusion Criteria:

(1) Active symptoms of mania or psychosis at baseline (based on ADIS-5); (2) depression with active suicidal ideation/intent that would preclude treatment (based on ADIS-5 & BDI-II); (3) moderate-to-severe cognitive impairment as indicated by a score below 20 on the SLUMS; (4) active drug/alcohol abuse during the initial 3-months of study enrollment (otherwise Veterans with comorbid substance/alcohol dependence are study eligible); and (5) undergoing concurrent transdiagnostic CBT for anxiety.

### **F2. Procedure**

## Recruitment

Several methods of recruitment will be used in the study. Letters will be sent to Veterans enrolled for care at the MEDVAMC, including those scheduled for appointments in outpatient clinics (e.g., General Mental Health, Primary Care, Post Deployment, PTSD). In addition, flyers advertising the study will be posted throughout MEDVAMC, community based outpatient clinics affiliated with MEDVAMC, and Vet centers located in Houston. We will also recruit from non-profit organizations serving Veterans in the Houston community (e.g., U.S. Vets). The study will also be advertised through electronic messaging boards throughout the hospital, Veterans newsletters such as the “VA Star,” and via free list-serves that Veterans subscribe to such as the “Houston Military Affairs” mail group.

## Assessments

Participants will undergo a total of four in-person assessments. A pre-screening will be conducted using the Q-LES-Q-SF to determine a moderate level of impairment in general functioning. Veterans obtaining an impairment score of 42 or lower will be study eligible and complete a full baseline evaluation. Data obtained from the Q-LES-Q-SF at the pre-screen will not be used for research purposes. If the Veteran meets inclusion criteria and agrees to participate, s/he will be consented and re-administered this measure, which takes approximately 5-10 minutes to complete. The baseline evaluation will occur approximately 1-2 weeks before treatment. The baseline evaluation will include a structured diagnostic interview (ADIS-5) and psychological screening measures to determine general emotional functioning and the presence of specific psychiatric disorders. During the pre-treatment appointment, it will be explained to the patient that all assessment and treatment sessions will be supervised by a licensed psychologist (PI). Patients will also be informed that study staff will need to access their medical records periodically to track relevant psychiatric and medical information. Protected health information that will be collected from Veterans in this study include: name, address, telephone numbers, dates of appointments related to the study, last four digits of social security number, and voice recordings. Demographic information, medications prescribed, and dates of mental health treatment appointments will also be collected. VA Quality Assurance and BCM IRB personnel responsible for providing general oversight of this study (e.g., patient enrollment and consent forms) may also have access to research data. Specific data that may be accessed include symptom measures collected during the course of the study. Study data regarding individual information that is not in the patient's medical record will remain confidential and inaccessible to other agencies. Health records of participants in this study will be flagged since they are participating in an intervention for a psychiatric disorder.

Assessments at four time points (baseline, 1-month, 3-month, and 6-month follow-up) will be conducted for all three conditions. Diagnostic assessments will be conducted by study staff being directly supervised by the PI or another licensed psychologist. All assessments will be conducted in individual sessions that will occur either at the MEDVAMC or over the telephone (no social security numbers will be requested from subjects or potential subjects via phone). Veterans will be provided opportunities for breaks during in-person assessments and two phone appointments will be scheduled to reduce fatigue effects. Should a participant need immediate attention (e.g., expresses active suicidal intent or psychosis) during the assessment, the PI will ensure that the patient is seen by a provider through the walk-in clinic at the MEDVAMC that same day. Follow-up assessments will be conducted by an evaluator masked to treatment assignment.

Participants will receive a modest amount of monetary compensation for study participation, as detailed in Section L.

## Assessment Battery

The assessment battery will consist of the following: (1) Community Reintegration of Injured Service members – Computer-Adaptive Test (CRIS-CAT), a commonly used measure of community reintegration following deployment; (2) Short-Form 12 Health Survey (SF-12), measures eight domains related to physical and mental health, health perceptions, and the impact of physical or emotional problems on general functioning via self-report; (3) Beck Anxiety Inventory (BAI) assesses the severity of anxiety symptoms, minimizing those that overlap with depression; (4) Beck Depression Inventory - Second Edition (BDI-II) assesses severity of depressive symptoms; (5) Quality of Life Enjoyment and Satisfaction Questionnaire- Short Form (Q-LES-Q-SF) is a brief, 16-item measure of subjective functioning and satisfaction across a range of life domains including work, leisure activities, social relationships, and physical health; (6) Saint Louis University Mental Status Exam (SLUMS) is an 11-item clinician-administered screening measure of cognitive impairment; (7) Anxiety Disorders Interview Schedule DSM-5 (ADIS-5) is a gold-standard semi-structured clinician interview used to assess for the presence of all anxiety disorders including PTSD. Modules examining the presence of psychosis, mood and

substance abuse disorders are also included; (8) Demographic and Military Survey is a brief questionnaire we have used in previous studies that inquires about general demographic and military information. Veterans are asked about their periods of service, deployment dates, whether they seek healthcare outside of VA, and other information pertaining to their education and employment history; (9) Perceived Barriers to Seeking Mental Health Services (PB-SMHS) assesses concerns specific to Veterans that are related to seeking mental health counseling and related services; and (10) Client Satisfaction Questionnaire-8 (CSQ-8) is a brief 8-item measure used to assess overall treatment satisfaction. All measures will be administered at each assessment period, except the ADIS-5, Q-LES-Q-SF, SLUMS, Demographic Questionnaire, and PB-SMHS, which will only be administered at baseline. The CSQ will only be administered at 1-month and 3-month follow-up periods. The complete battery of assessments can be administered in 2-3 hours.

#### Treatments

Participants will be randomly assigned to one of three treatment arms (iCBT, sCBT, TAU), described in detail below. Both iCBT and sCBT treatments are identical except for delivery format. Persons delivering the treatment will include a masters-level and doctoral-level interventionist who will be trained to deliver treatments in both intervention conditions under the supervision of [name], a licensed psychologist and co-investigator on this project. [name] is experienced in transdiagnostic treatment for anxiety and in the delivery of exposure-based treatments for anxiety disorders with Veterans. She will work closely with the interventionists to ensure that all patients are closely monitored, with their safety taking priority above the needs of the study. Our pilot work with Veterans at the MEDVAMC and community based outpatient clinics demonstrates the intensive weekend format to be a safe mode of treatment delivery. However, as an added level of precaution, the MEDVAMC has an emergency department with an on-call psychiatrist available 24 hours a day in the unlikely event that a patient needs immediate medical intervention.

**Standard Cognitive Behavioral Treatment:** The sCBT condition consists of 12 treatment sessions delivered once weekly over a 12-week period. Duration of sessions will be approximately 90 minutes, depending on the session module. For example, psychoeducation sessions typically last 60 minutes, whereas cognitive restructuring and exposure sessions typically last up to 90 minutes. Thus, the entire treatment requires approximately 16 hours of direct patient contact. A maximum of 6 Veterans may be enrolled per group cycle. The transdiagnostic treatment protocol consists of (1) psychoeducation about the general treatment structure, the nature of anxiety disorders and co-occurring symptoms such as depression, and physiology underlying the fight/flight response; (2) cognitive restructuring, a method of challenging maladaptive thoughts that maintain negative affect and fears by examining evidence that replaces catastrophizing and overestimations in thinking; and (3) exposure to feared stimuli through imaginal, interoceptive, or in-vivo exercises. Treatment concludes with relapse prevention planning. Homework is completed regularly over the course of treatment. Patients will be asked to monitor and record their anxiety and mood symptoms, complete thought records, and engage in exposure exercises.

**Intensive Cognitive Behavioral Treatment:** The iCBT condition will contain the same treatment components as sCBT, but the intervention will be delivered over one weekend, lasting 8 hours each day (see weekend itinerary in Section S: file named "H42354 Study Measures"). A maximum of 6 Veterans may be enrolled per group cycle. Veterans will be asked to complete practice assignments using thought records during the treatment. They will also be asked to monitor and record their anxiety and mood outside of treatment.

**Treatment As Usual:** The TAU condition consists of routine clinical care patients would typically receive at the MEDVAMC. This may include medication management alone (visits once every 4 months, on average) or in conjunction with other forms of individual or group therapies that involve supportive counseling or educational and skills-based classes (e.g., anger management, PTSD Recovery 101, etc.). These time-limited classes typically occur once per week for a total of 8 – 12 weeks. The TAU condition may also include Veterans who participate in disorder-specific evidence-based interventions such as cognitive-processing therapy or prolonged exposure therapy, as these treatments reflect the current standard of routine care in VA. Information on participants' engagement in these and all other forms of mental health treatment during the study will be collected via self-report and chart review. This information will be examined and if needed, will be controlled for in subsequent analyses. Upon completing the 6-month follow-up, patients in this condition will be offered iCBT or sCBT.

#### Interviews

A maximum of 40 Veterans who completed iCBT and their family members will be invited to participate in a

qualitative interview. The purpose of the interview is to obtain Veteran perspectives on the iCBT format. Using an interview guide (see Section S file named "H42354 Study Measures," the PI or another study staff member will conduct in-person interviews at the MEDVAMC approximately 1-month after completing treatment. The inclusion of up to 40 Veterans will be ample to achieve theoretical saturation concerning the impact of iCBT on the recovery process. Veterans will provide written informed consent (and sign a release of information form for family members present) before interviews begin and be compensated \$25 upon completion. All interviews will be digitally audio-recorded using a microphone linked directly to a VA networked computer. De-identified audio recordings of the interviews will be saved to the MEDVAMC Research folder on the S Drive: Research-Data/[name] Lab/H42354 Transdiagnostic.

## **Section G: Sample Size/Data Analysis**

### **G1. Sample Size**

How many subjects (or specimens, or charts) will be used in this study?

Local: 335      Worldwide: 335

Please indicate why you chose the sample size proposed:

A total of 335 participants will be recruited for this study: 252 Veterans will be recruited to participate in the RCT; 40 Veterans who participated in iCBT and their family members (up to 40) will be invited to participate in the qualitative interview.

For the RCT, a total of 252 patients will be randomized across the 3 arms (95 to iCBT, 95 to sCBT, and 62 to TAU) to have 80% power to detect differences among groups in the primary outcomes. A recent meta-analysis of transdiagnostic treatment for anxiety demonstrated a medium effect size ( $g=.69$ ) on quality of life outcomes. Based on these findings, we are using a more conservative effect size of 0.50 to calculate the sample size that will need to be recruited and randomized to draw conclusions. We will use unequal randomization to the active intervention arms and to treatment as usual to reduce unnecessary recruitment. We also inflated the sample size to account for intraclass correlations among patients and for attrition and loss to follow-up in order to obtain the number that must be recruited for the study. The recruited sample size of 95 for iCBT and 95 for sCBT, assuming 20% attrition at 1 month and accounting for clustering of patients within therapists, will result in 49 patients per group for analysis. For our primary analyses, this sample size will have 80% power to detect a medium effect size of .57 using a two-group t-test with  $\alpha=.05$  two-sided significance level.

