### **G2. Data Analysis**

Provide a description of your plan for data analysis. State the types of comparisons you plan (e.g. comparison of means, comparison of proportions, regressions, analysis of variance). Which is the PRIMARY comparison/analysis? How will the analyses proposed relate to the primary purposes of your study?

For our primary analyses, we will compare changes between the iCBT, sCBT, and TAU groups at all time periods in a single regression using a hierarchical mixed-model analysis. Because the number of patients randomized to the 3 groups is not equal, we will test for unequal variances and if necessary, will account for this in our regression models. For outcomes with unequal variances, in the mixed model, we will estimate the variances separately and adjust the degrees of freedom for the unequal variances. A priori covariates will also be included in the model. A significant time-by-treatment interaction will be followed by pairwise contrasts to determine whether the active interventions differed from TAU and whether the active treatments differed from each other. We will report the p-values and adjust p-values post-hoc using multiple comparisons procedures (e.g., Bonferroni) as recommended in the literature. For secondary analyses, we will run hierarchical linear regression models for each outcome using the baseline and 1 month data and with the a priori covariates. Hierarchical logistic regression models will be used to test differences in treatment engagement across conditions.

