Hypothesis 1b: *iCBT will result in improved reintegration/quality of life measures relative to sCBT at 1-month follow-up.* Only patients in the iCBT and sCBT groups will be used in the analyses. For each outcome, we will run a hierarchical linear regression model using the baseline and 1 month data and with the *a priori* covariates and anxiety disorder stratification variables. Patients will be nested within therapist. The models will contain the 1 month value as the outcome variable and the baseline value of the outcome as an additional covariate. A significant value for the parameter estimate for the intervention will indicate that the iCBT and sCBT groups differed at 1 month.

Specific Aim 2: Examine the effectiveness of iCBT in reducing anxiety/depression symptoms relative to sCBT and TAU. **Hypothesis 2a:** *iCBT and sCBT will significantly reduce anxiety and depression symptoms relative to TAU at 3-and 6- month follow-ups.* The analyses described for hypothesis 1a will be repeated for this hypothesis using the secondary outcomes. Anxiety will be measured using the BAI and depression measured using the BDI-II. **Hypothesis 2b:** *iCBT will result in improved anxiety/depression measures relative to sCBT at 1-month follow-up.* The analyses described for hypothesis 1b will be repeated for this hypothesis using the secondary outcomes.

Specific Aim 3 (Exploratory): Hypothesis 3a: *Compare rates of psychotherapy engagement in iCBT relative to sCBT.* We will use hierarchical logistic regression models to test if the iCBT and sCBT groups differed on treatment engagement (defined as the percentage of randomized patients who participated in 12 or more treatment hours). The outcome will be whether or not

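### G1 says an effect of 0.50 set the sample size, but the only calculation it shows gives 80% power at about 0.57, and nothing reconciles the two

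*Protocol*

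**What the plan says.** All the sample-size text is in protocol section G1; the SAP contains none. G1 randomises 252 Veterans, 95 to iCBT, 95 to sCBT and 62 to TAU, "to have 80% power to detect differences among groups in the primary outcomes". It cites a meta-analytic effect of g = .69 on quality of life and then says "we are using a more conservative effect size of 0.50 to calculate the sample size that will need to be recruited and randomized". It adds: "We also inflated the sample size to account for intraclass correlations among patients and for attrition and loss to follow-up".

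The paragraph closes with one worked figure. The 95 per active arm, "assuming 20% attrition at 1 month and accounting for clustering of patients within therapists, will result in 49 patients per group for analysis". For the primary analyses, "this sample size will have 80% power to detect a medium effect size of .57 using a two-group t-test" at a two-sided .05 level.

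G1 does not explain the move from 0.50 to .57 and gives no power at 0.50. It does not say whether 0.50 refers to iCBT vs sCBT, to an active arm vs TAU, or to both active arms vs TAU. It gives no effective size for TAU, no intraclass correlation and no cluster size.

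**The concern.** If 0.50 fixed the number randomised, and that number was already inflated for clustering and attrition, then removing the same losses should bring the detectable effect back to about 0.50. It comes back at .57 instead. For the one contrast G1 works through, the size it arrives at does not match the effect it says it started from.

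G1 is where a reader learns what the trial can detect. Someone who takes 0.50 as the design basis would overstate the sensitivity of the iCBT vs sCBT comparison, and could read a null result as excluding more than the shown calculation supports.

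**Working it through.** **Inputs, all from G1:** 95 randomised per active arm and 62 to TAU; 20% attrition at 1 month; 49 effective per active arm; effects 0.50 and .57; two-group t-test, two-sided α = .05.

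**Method.** Noncentral t. For arms of size n₁ and n₂ and standardised effect d, the noncentrality is δ = d·√[n₁n₂/(n₁+n₂)] with n₁+n₂−2 degrees of freedom. Power is the probability of exceeding the two-sided critical value.

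**1. Reproduce G1's figure.** With 49 per arm, √(49×49/98) = √24.5 = 4.950. At d = 0.57, δ = 2.821 and power is 79.8%. The effect detectable with exactly 80% is 0.572. G1's statement holds.

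**2. Same test at 0.50.** δ = 0.50 × 4.950 = 2.475, and power is 68.8%.

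**3. Size needed for 0.50.** 63 per arm gives 79.5% and 64 gives 80.1%, so 64 effective per arm are needed against 49.

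**4. Could a different reading of the same inputs explain it?**
- 95 × 0.8 = 76 per arm after attrition, and 76/49 = 1.55 is the implied design effect (back-calculated, not stated).
- Ignoring clustering, 76 per arm gives 86.5% at 0.50, but G1 says clustering was taken into account.
- A one-sided .05 test with 49 per arm gives 79.2% at 0.50, but G1 says two-sided.

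**5. Baseline adjustment.** The SAP's 1-month iCBT vs sCBT model adjusts for baseline: "The models will contain the 1 month value as the outcome variable and the baseline value of the outcome as an additional covariate". As an approximation, this replaces d by d/√(1−r²), where r is the baseline-outcome correlation. The documents give no r, so the values below are assumptions (49 per arm, d = 0.50).

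| r | Power |
|---|---|
| 0.3 | 72.9% |
| 0.4 | 76.2% |
| 0.5 | 80.8% |
| 0.6 | 86.5% |

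80% is reached at r = √[1 − (0.50/0.5717)²] = 0.485, or about 0.49.

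**6. Contrasts with TAU at 0.50.** G1 gives no calculation, so these are illustrations. They assume that the 20% attrition also applies to TAU (62 × 0.8 = 49.6) and, where clustering is applied to TAU as well, an effective size of 49.6/1.551 = 32.

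| Reading | One active arm vs TAU | Both active arms pooled vs TAU |
|---|---|---|
| Clustering in active arms and TAU | 49 vs 32: 58% | 98 vs 32: 68% |
| Clustering in active arms only | 49 vs 49.6: 69% | 98 vs 49.6: 81% |
| Attrition only | 76 vs 49.6: 78% | 152 vs 49.6: 86% |

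Whether 0.50 is met against TAU therefore depends on a reading that the documents do not settle.

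**The case against.** The strongest reply is that there may be no contradiction. G1 attaches 80% power explicitly only to .57; the sentence with 0.50 names neither a power nor a contrast. The 0.50 is scaled down from a meta-analysis of treatment effects and sits next to the text on the smaller TAU arm, whereas .57 follows directly from the two active-arm sizes. So 0.50 may belong to a comparison with TAU and .57 to iCBT vs sCBT. The SAP's Hypothesis 1a sets both active treatments against TAU, and the pooled reading with clustering in the active arms only does pass 80% at 0.50. This reply stands far enough that 0.50 should not simply be struck out: it may be the true basis for another contrast. It does not remove the point. G1 neither says this nor shows the calculation, and it presents 0.50 as the basis for the whole number randomised.

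Four stronger readings are tempting, and the documents support none of them:
- *A reader might infer that .57 is a miscalculation.* It reproduces.
- *A reader might infer that the trial has 69% power.* That figure is for the unadjusted t-test at 0.50. The planned models are covariate-adjusted, and with r above about 0.49 the 1-month comparison would pass 80%.
- *A reader might infer that the TAU contrasts also fall short at 0.50.* Every single-arm reading above does, but two of the three pooled readings do not.
- *A reader might infer that multiplicity lowers the 1-month figure further.* G2 says "We will report the p-values and adjust p-values post-hoc using multiple comparisons procedures (e.g., Bonferroni) as recommended in the literature", but this follows the three-arm time-by-treatment interaction. The SAP's 1-month iCBT vs sCBT model has a single treatment parameter and no stated adjustment of that kind.

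It is also fair to say that .57 appears in the same paragraph, so an attentive reader will see it. That bears on severity rather than on whether the text is right.

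**Conclusion.** Wrong as written; low severity. The effect that G1 names as the basis of its sample size is not the one delivered by the only calculation it shows: 80% power is reached at about 0.57, against about 69% at 0.50, a shortfall of about 11 points. This conclusion uses only figures and the test stated in G1. The finding is an unreconciled design basis. It does not show that the trial is underpowered: power of the planned models at 0.50 may lie above or below 80%, because it depends on a correlation and on a choice of contrast that the documents do not give.

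**What to change.** Keep 95 per active arm and revise G1 in two steps.

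First, tie the worked figure to its contrast, for example:

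> With 95 randomised per active arm, about 76 are expected to have 1-month data after 20% attrition, equivalent to 49 per arm after allowing for clustering within therapists (ICC = [value], cluster size = [value]). By an unadjusted two-sided 0.05 t-test this gives 80% power for a difference of 0.57 between iCBT and sCBT at 1 month, and about 69% for 0.50.

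Second, either correct the sentence saying that 0.50 set the sample size, or keep 0.50 and state the contrast and calculation for which it gives 80%. That means the effective size of each group compared and any baseline-outcome correlation relied on, with its justification. For iCBT vs sCBT at 1 month, that correlation would have to be about 0.49.

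The cost is wording in G1 only, and the number randomised, the analysis and the conduct do not change. The stated sensitivity for iCBT vs sCBT becomes slightly less favourable, 0.57 instead of 0.50.
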